#### **4.3.2.1 Dose Modifications for Grade 3 Cardiac Arrhythmias**

The actions described below should be followed for the indicated following drug-related toxicities (Table 4-2):

- Grade 3 cardiac arrhythmias

Table 4-2 Dose Modification Actions for Grade 3 Cardiac Arrhythmias	
Occurrence	Action
First	Hold ibrutinib until recovery to ≤ Grade 1 or baseline; restart at 420 mg dose
Second	Discontinue ibrutinib

 When ibrutinib doses are held they will not be made up – study assessments will continue as originally scheduled. Ibrutinib may be held for a maximum of 28 consecutive days at a time. Study treatment should be permanently discontinued in the event of a toxicity lasting >28 days. Once the ibrutinib is reduced it cannot be re-escalated.

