#### **4.3 Toxicity Management & Dosing Holds/Dose Modifications**

##### **4.3.1 Dose Holds**

At each study visit (see section 5.0 for schedule), the subject will be evaluated for possible drug toxicities. All previously established or new toxicities observed at any time are to be recorded in the appropriate electronic case report form (eCRF) and managed as described below. The lead principal investigator and QAM should be contacted regarding any unmanageable toxicity.

Study drug may be held for a maximum of 28 consecutive days. Once the ibrutinib dose is reduced, it cannot be re-escalated. When a dose is missed or held, it will not be made up, regardless of duration.

Observations and scheduled assessments will continue regardless of amount of drug the patient has had and should always be based on time from C1D1. (For example, if a patient is held on C2D14 for a week, the day they re-start will be C2D21, and the patient will still have scheduled assessments as planned on C3D1) Please contact QA if you have any questions on timing of holds or study assessments.

*See section 4.4.3 for subjects requiring the initiation of anticoagulants while receiving study drug and for instructions on dose modifications or temporary hold during concomitant administration of CYP3A4/5 inhibitors or inducers. For guidance on dose hold during the perioperative period for subjects who require surgical intervention or an invasive procedure while receiving study drug please see section 4.4.4.*

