##### **4.3.2 Dose Modifications**

The actions described below should be followed for the indicated drug- related toxicities per Table 4-1:

- Grade 3 (ANC <1000/mm^3) or Grade 4 neutropenia (ANC <500/mm^3)
- Grade 3 thrombocytopenia (platelets <50,000/mm^3) in the presence of significant bleeding
- Grade 4 thrombocytopenia (platelets <25,000/mm^3)
- Grade 3 or 4 neutropenia with infection or fever
- All other Grade 4 hematological toxicities
- Grade 3 or Grade 4 non-hematological toxicities including nausea, vomiting or diarrhea (if persistent despite optimal antiemetic or antidiarrheal therapy), exceptions noted below for cardiac related toxicities (see [Sections 4.3.2.1 & Section 4.3.2.1.1](#))
- Grade 2 cardiac failure
- Any unmanageable Grade 2 or Grade 3 drug-related toxicities. The PI should be contacted in these cases.

Table 4-1 Dose Modification Actions	
Occurrence	Action
First	Hold ibrutinib until recovery to ≤ Grade 1 or baseline; restart at 420 mg dose
Second	Hold ibrutinib until recovery to ≤ Grade 1 or baseline; restart at 280 mg dose
Third	Discontinue ibrutinib

 When ibrutinib doses are held they will not be made up – study assessments will continue as originally scheduled. Ibrutinib may be held for a maximum of 28 consecutive days at a time. Study treatment should be permanently discontinued in the event of a toxicity lasting >28 days. Once the ibrutinib is reduced it cannot be re-escalated.

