##### **4.4.3 Concomitant Medications/Treatments Requiring Special Precautions**

###### **4.4.3.1 CYP3A4/5 Inhibitors/Inducers**

Study Numbers: NU 14H06  
PCI-32765MCL2003Initial version: September 24, 2014  
AMD 11: ver. date 08.06.2022

Ibrutinib is metabolized primarily by CYP3A4/5. The clinical significance of the potential drug-drug interaction with strong CYP3A4/5 inhibitors in oncology subjects is currently not known. Due to this potential increase in ibrutinib exposure, concomitant use of strong CYP3A4/5 inhibitors (such as, indinavir, nelfinavir, ritonavir, saquinavir, clarithromycin, telithromycin, ketoconazole, itraconazole, and nefazodone; see Appendix I for a comprehensive list of such medications) should be avoided while the subject is receiving treatment and at least 14 days prior to registration. Moderate CYP3A4/5 inhibitors (aprepitant, erythromycin, fluconazole, verapamil, and diltiazem) should be used with caution. Grapefruit juices, Star fruit, and Seville oranges may also increase ibrutinib plasma concentrations and should be avoided for the duration of ibrutinib treatment.

If use of a strong CYP3A inhibitor is indicated, selection of an alternate concomitant medication with less potent enzyme inhibition potential is strongly recommended. If ibrutinib must be administered with a strong or moderate CYP3A inhibitor, refer to Table 4-3 for recommended dose modifications for ibrutinib, and notify the PI and NU Quality Assurance Monitor (QAM). Subjects should be monitored closely for potential treatment-related toxicities. After discontinuation of the CYP3A inhibitor, the same dose of ibrutinib that was administered prior to the temporary hold may be given upon reinitiation of ibrutinib.

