**Table 4-3: Dose Modifications for Use with CYP3A Inhibitors**

Patient Population	Coadministered Drug	Recommended Ibrutinib Dose
B-Cell Malignancies	• Moderate CYP3A inhibitor	280 mg once daily  Modify dose as recommended per Table 4-1, Table 4-2 and Section 4.3.2.1.1.
	• Voriconazole 200 mg twice daily • Posaconazole suspension 100 mg once daily, 100 mg twice daily, or 200 mg twice daily	140 mg once daily  Modify dose as recommended per Table 4-1, Table 4-2 and Section 4.3.2.1.1.
	• Posaconazole suspension 200 mg three times daily or 400 mg twice daily • Posaconazole IV injection 300 mg once daily • Posaconazole delayed-release tablets 300 mg once daily	70 mg once daily  Interrupt dose as recommended per Table 4-1, Table 4-2 and Section 4.3.2.1.1..
	• Other strong CYP3A inhibitors	Avoid concomitant use.  If these inhibitors will be used short-term (such as anti-infectives for seven days or less), interrupt ibrutinib.
	• Moderate CYP3A inhibitor	420 mg once daily  Modify dose as recommended per
Chronic Graft versus Host Disease		

Study Numbers: NU 14H06  
PCI-32765MCL2003Initial version: September 24, 2014  
AMD 11: ver. date 08.06.2022

		Table 4-1, Table 4-2 and Section 4.3.2.1.1..
	
 
• Voriconazole 200 mg twice daily
 
• Posaconazole suspension 100 mg once daily, 100 mg twice daily, or 200 mg twice daily
 
	280 mg once daily  Modify dose as recommended per Table 4-1, Table 4-2 and Section 4.3.2.1.1..
	
 
• Posaconazole suspension 200 mg three times daily or 400 mg twice daily
 
• Posaconazole IV injection 300 mg once daily
 
• Posaconazole delayed-release tablets 300 mg once daily
 
	140 mg once daily  Modify dose as recommended per Table 4-1, Table 4-2 and Section 4.3.2.1.1..
	
 
• Other strong CYP3A inhibitors
 
	Avoid concomitant use.  If these inhibitors will be used short-term (such as anti-infectives for seven days or less), interrupt ibrutinib.

Coadministration of ibrutinib with strong CYP3A4/5 inducers (such as carbamazepine and rifampin) may decrease ibrutinib plasma concentrations and should be avoided. A comprehensive list of inhibitors, inducers, and substrates is provided in a link in Appendix I.

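### The fixed restart doses in Tables 4-1 and 4-2 conflict with other dosing rules for patients already below the printed dose

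*Combined protocol and SAP*

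**What the plan says.** The starting dose is 560 mg daily (Section 4.2). Three tables can change it.

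- **Table 4-1** (Section 4.3.2, general drug-related toxicities): first occurrence, hold and restart at 420 mg; second occurrence, "Hold ibrutinib until recovery to ≤ Grade 1 or baseline; restart at 280 mg dose"; third, discontinue.
- **Table 4-2** (Section 4.3.2.1, Grade 3 arrhythmias): first occurrence, "Hold ibrutinib until recovery to ≤ Grade 1 or baseline; restart at 420 mg dose"; second, discontinue. Section 4.3.2 separates these events from Table 4-1 with the words "exceptions noted below for cardiac related toxicities".
- **Table 4-3** (Section 4.4.3.1, B-cell malignancies): 280 mg with a moderate CYP3A inhibitor; 140 mg with voriconazole or the lower posaconazole suspension doses. Both rows then say "Modify dose as recommended per Table 4-1, Table 4-2", with a further reference to Section 4.3.2.1.1.

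Footnote 1, attached to the Action column of both Tables 4-1 and 4-2, says "Once the ibrutinib is reduced it cannot be re-escalated". Section 4.3.1 has the same rule: "Once the ibrutinib dose is reduced, it cannot be re-escalated". On stopping an inhibitor, Section 4.4.3.1 says that "the same dose of ibrutinib that was administered prior to the temporary hold may be given upon reinitiation of ibrutinib".

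**The concern.** The restart doses are absolute amounts, not steps relative to the dose being taken. They work for a patient who starts from 560 mg and meets only Table 4-1. A patient already below the printed dose gets an instruction that clashes with another rule.

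For a patient on a continuing inhibitor, the clash is between the restart cell and the dose Table 4-3 has set because of the interaction. For a patient already reduced twice under Table 4-1, it is between the Table 4-2 cell and its own footnote.

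The stake is the dose given after a drug-related toxicity that was serious enough to interrupt treatment. Read literally, the cell can name a higher dose than the one on which the toxicity occurred. Read with the footnote, it names no dose, and sites may resolve that differently. Both situations are foreseeable: Section 1.2.3 lists atrial fibrillation among the commonest Grade 3 or 4 non-hematological reactions (at least 5%), and Section 4.4.3.1 provides for giving ibrutinib with an inhibitor where this cannot be avoided. The documents do not say how many patients would be affected. Sample size, alpha and power are not involved.

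**Working it through.** The plan states no figure to reproduce. The check compares each printed restart dose with the dose being taken at the event.

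**Inputs.** Start 560 mg (Section 4.2). Table 4-1: 420 mg, then 280 mg. Table 4-2: 420 mg. Table 4-3: 280 or 140 mg.

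**Formula.** Ratio = printed restart dose / current dose. A ratio above 1 means the cell names an increase.

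**A. Inhibitor continuing, patient on the Table 4-3 dose**

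| Current dose | Table 4-1, first | Table 4-1, second | Table 4-2, first |
|---|---|---|---|
| 280 mg | 420/280 = 1.5 | 280/280 = 1.0 | 420/280 = 1.5 |
| 140 mg | 420/140 = 3.0 | 280/140 = 2.0 | 420/140 = 3.0 |

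Five of the six cells exceed the Table 4-3 dose. The first-occurrence conflict does not depend on how occurrences are counted, because a first event is first under any rule.

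**B. No inhibitor, occurrences counted separately by table**

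| Event | Earlier events | Ratio |
|---|---|---|
| Table 4-1, first | none | 420/560 = 0.75 |
| Table 4-1, second | one Table 4-1 | 280/420 = 0.67 |
| Table 4-1, first | one Table 4-2 | 420/420 = 1.0 |
| Table 4-1, second | one Table 4-1, one Table 4-2 | 280/420 = 0.67 |
| Table 4-2, first | none | 420/560 = 0.75 |
| Table 4-2, first | one Table 4-1 | 420/420 = 1.0 |
| Table 4-2, first | two Table 4-1 | 420/280 = 1.5 |

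One of the seven situations names an increase: 280 mg to 420 mg. If occurrences were counted across both tables, that patient would be at a third occurrence and would stop, so the conflict would not arise.

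**C. Does the ban on re-escalation settle it?** In B it does forbid 420 mg, since the earlier reductions were for toxicity. The cell and the footnote then contradict each other, and no section supplies a replacement dose. In A the text is open. Section 4.3.1 states the ban without qualification, while the sentence in Section 4.4.3.1 on resuming the earlier dose concerns a temporary hold after the inhibitor has stopped. Neither addresses a toxicity restart while the inhibitor continues.

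**D. With a cap.** Restart = min(printed dose, current dose). The situation in B becomes min(420, 280) = 280 mg. The cells in A become 280 mg or 140 mg. Every flagged ratio becomes 1.0, so no increase remains. This follows by construction. A ratio of 1.0 also means no reduction after the toxicity.

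**The case against.** The strongest reply is that the safeguard already exists. Footnote 1 belongs to every action cell, and Section 4.3.1 repeats the ban with no exception by reason for reduction. No careful investigator would triple the dose of a patient on voriconazole who has just had a toxicity. Section 4.4.3.1 also requires close monitoring and notice to the PI and the quality assurance monitor when ibrutinib is given with a strong or moderate inhibitor, and Section 4.8 lets the investigator withdraw a patient for safety.

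Much of this stands. A reader might infer that the protocol has no cap and orders re-escalation after a toxicity reduction; the footnote and Section 4.3.1 rule that out. For the twice-reduced patient, the fault is a cell that contradicts its footnote and leaves the dose blank. That case also needs an uncommon sequence and separate counting by table. *Occurrence* is not defined, although the separate tables and the cardiac exception in Section 4.3.2 make separate counting the natural reading.

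The reply is weaker for the inhibitor case. The reach of the ban to reductions made only for an inhibitor is unstated, and notification supplies no restart dose. Equally, the documents do not support saying that this case breaches the ban.

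A reader might also extend the point to the 70 mg row of Table 4-3, either as a larger multiple or as a dose that 140 mg capsules cannot deliver. That row tells sites to interrupt, not modify, so only the hold may apply. Supply details are left to a Drug Management Plan that is not among the documents. Neither extension is made here.

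**Conclusion.** The concern holds as a conflict between dosing instructions, not as a missing safeguard. Its firmer part is the continuing-inhibitor case: the printed first-occurrence dose is 1.5 or 3 times the Table 4-3 dose, and the printed second-occurrence dose is 2 times that dose for a patient on 140 mg. This assumes that the inhibitor continues and that the patient is on the Table 4-3 dose at the event.

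The second part is one situation, 420 mg printed for a patient at 280 mg (1.5 times). It rests on separate counting by table, and the footnote already forbids the increase, so the remaining defect is that no usable dose is named.

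The counts of 5 in 6 and 1 in 7 describe table cells. A reader might take them as a measure of patient risk, but the documents give no frequencies that would support that. Table 4-1 used alone from 560 mg, with no inhibitor, is consistent. A correction is worthwhile because the instruction governs dosing after toxicity and the change is small.

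**What to change.** In both tables, replace the restart wording with: *restart at the stated dose or the dose being taken at the time of the event, whichever is lower; while a CYP3A inhibitor continues, never above the Table 4-3 dose.* Add one sentence saying whether occurrences are counted across Tables 4-1 and 4-2. Keep the existing discontinuation rules.

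The cost is a short amendment to Section 4 and notice to the sites; visits and sample size do not change. The limitation is that the cap only prevents an increase: in the flagged cases the patient restarts at the dose on which the toxicity occurred. The sponsor's medical team should therefore decide, in the same amendment, whether these patients step down further or discontinue.

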#### **4.3.2.1.1 Dose Modifications for Grade 3 and higher Cardiac Failure & Grade 4 Cardiac Arrhythmias**

**Ibrutinib is to be discontinued** if the following drug related toxicities occur:

- Grade 3 or 4 cardiac failure
- Grade 4 cardiac arrhythmias

#### **4.3.3 Lymphocytosis**

Upon initiation of ibrutinib, a temporary increase in lymphocyte counts (i.e., ≥ 50% increase from baseline and above absolute count 5,000/mcL) occurred in 33% of relapsed/refractory MCL treated with ibrutinib in the MCL registration trial (PCYC1104). This onset of isolated lymphocytosis occurs during the first few weeks of ibrutinib therapy and resolves by a median of 8 weeks. Patients with MCL who develop lymphocytosis greater than 400,000/mcL have developed intracranial hemorrhage, lethargy, gait instability and headache. However, some of these cases

were in the setting of disease progression.

#### **4.4 Concomitant Medications/Treatments**

All concomitant therapies must be recorded in the appropriate eCRF and source documents throughout the study, beginning with the time of written informed consent up to 30 days after the last dose of study drug.

##### **4.4.1 Permitted Concomitant Medications/Treatments**

- Standard supportive care therapies (e.g., antiemetics, loperamide) needed for the management of symptoms are permitted, as clinically indicated.
- Hematopoietic growth factors may be administered according to institutional guidelines
- Hormonal birth control is permitted.

##### **4.4.2 Prohibited Concomitant Medications/Treatments**

The following medications are prohibited during the study:

- Any chemotherapy
- Anticancer immunotherapy
- Chronic use of systemic corticosteroids above prednisone 10mg p.o. daily (or equivalent dose of other corticosteroid)
- Experimental therapy
- Radiotherapy

##### **4.4.3 Concomitant Medications/Treatments Requiring Special Precautions**

###### **4.4.3.1 CYP3A4/5 Inhibitors/Inducers**

Study Numbers: NU 14H06  
PCI-32765MCL2003Initial version: September 24, 2014  
AMD 11: ver. date 08.06.2022

Ibrutinib is metabolized primarily by CYP3A4/5. The clinical significance of the potential drug-drug interaction with strong CYP3A4/5 inhibitors in oncology subjects is currently not known. Due to this potential increase in ibrutinib exposure, concomitant use of strong CYP3A4/5 inhibitors (such as, indinavir, nelfinavir, ritonavir, saquinavir, clarithromycin, telithromycin, ketoconazole, itraconazole, and nefazodone; see Appendix I for a comprehensive list of such medications) should be avoided while the subject is receiving treatment and at least 14 days prior to registration. Moderate CYP3A4/5 inhibitors (aprepitant, erythromycin, fluconazole, verapamil, and diltiazem) should be used with caution. Grapefruit juices, Star fruit, and Seville oranges may also increase ibrutinib plasma concentrations and should be avoided for the duration of ibrutinib treatment.

If use of a strong CYP3A inhibitor is indicated, selection of an alternate concomitant medication with less potent enzyme inhibition potential is strongly recommended. If ibrutinib must be administered with a strong or moderate CYP3A inhibitor, refer to Table 4-3 for recommended dose modifications for ibrutinib, and notify the PI and NU Quality Assurance Monitor (QAM). Subjects should be monitored closely for potential treatment-related toxicities. After discontinuation of the CYP3A inhibitor, the same dose of ibrutinib that was administered prior to the temporary hold may be given upon reinitiation of ibrutinib.

**Table 4-3: Dose Modifications for Use with CYP3A Inhibitors**

Patient Population	Coadministered Drug	Recommended Ibrutinib Dose
B-Cell Malignancies	• Moderate CYP3A inhibitor	280 mg once daily  Modify dose as recommended per Table 4-1, Table 4-2 and Section 4.3.2.1.1.
	• Voriconazole 200 mg twice daily • Posaconazole suspension 100 mg once daily, 100 mg twice daily, or 200 mg twice daily	140 mg once daily  Modify dose as recommended per Table 4-1, Table 4-2 and Section 4.3.2.1.1.
	• Posaconazole suspension 200 mg three times daily or 400 mg twice daily • Posaconazole IV injection 300 mg once daily • Posaconazole delayed-release tablets 300 mg once daily	70 mg once daily  Interrupt dose as recommended per Table 4-1, Table 4-2 and Section 4.3.2.1.1..
	• Other strong CYP3A inhibitors	Avoid concomitant use.  If these inhibitors will be used short-term (such as anti-infectives for seven days or less), interrupt ibrutinib.
	• Moderate CYP3A inhibitor	420 mg once daily  Modify dose as recommended per
Chronic Graft versus Host Disease		

Study Numbers: NU 14H06  
PCI-32765MCL2003Initial version: September 24, 2014  
AMD 11: ver. date 08.06.2022

		Table 4-1, Table 4-2 and Section 4.3.2.1.1..
	
 
• Voriconazole 200 mg twice daily
 
• Posaconazole suspension 100 mg once daily, 100 mg twice daily, or 200 mg twice daily
 
	280 mg once daily  Modify dose as recommended per Table 4-1, Table 4-2 and Section 4.3.2.1.1..
	
 
• Posaconazole suspension 200 mg three times daily or 400 mg twice daily
 
• Posaconazole IV injection 300 mg once daily
 
• Posaconazole delayed-release tablets 300 mg once daily
 
	140 mg once daily  Modify dose as recommended per Table 4-1, Table 4-2 and Section 4.3.2.1.1..
	
 
• Other strong CYP3A inhibitors
 
	Avoid concomitant use.  If these inhibitors will be used short-term (such as anti-infectives for seven days or less), interrupt ibrutinib.

Coadministration of ibrutinib with strong CYP3A4/5 inducers (such as carbamazepine and rifampin) may decrease ibrutinib plasma concentrations and should be avoided. A comprehensive list of inhibitors, inducers, and substrates is provided in a link in Appendix I.

#### 4.4.3.2 Antiplatelet Agents and Anticoagulants

There have been reports of hemorrhagic events in subjects treated with ibrutinib, both with and without thrombocytopenia. These include minor hemorrhagic events such as contusion, epistaxis and petechiae; and major hemorrhagic events including gastrointestinal bleeding, intracranial hemorrhage, and hematuria. Also, patients with congenital bleeding diathesis have not been studied.

Warfarin or vitamin K antagonists should not be administered concomitantly with ibrutinib. Supplements such as fish oil and vitamin E preparations should be avoided. Ibrutinib should be withheld at least 3 to 7 days pre- and post-surgery depending upon the type of surgery and the risk of bleeding (see Section prohibitions and restrictions).

Ibrutinib should be used with caution in subjects requiring other anticoagulants or medications that inhibit platelet function. It is possible that treatment with ibrutinib may increase the risk of bruising or bleeding, particularly in subjects receiving antiplatelet agents or anticoagulants. Subjects receiving antiplatelet agents in conjunction with ibrutinib should be observed closely for any signs of bleeding and ibrutinib should be held in the event of major bleeding events defined as adverse event of special interest (Section 7.2.5).

#### 4.4.4 Precautions & Restrictions Regarding Surgical Interventions or Procedures

Study Numbers: NU 14H06  
PCI-32765MCL2003Initial version: September 24, 2014  
AMD 11: ver. date 08.06.2022

The following guidance should be applied during the perioperative period for subjects who require surgical intervention or an invasive procedure while receiving ibrutinib:

- For any planned surgery or invasive procedure requiring sutures or staples for closure, ibrutinib should be held at least 7 days prior to the intervention and at least 7 days after the procedure, and restarted at the discretion of the treating investigator when the surgical site is reasonably healed without serosanguineous drainage or the need for drainage tubes.
- For minor planned procedures (such as a central line placement, needle biopsy, thoracentesis, or paracentesis), ibrutinib should be held for at least 3 days prior to the procedure and should not be restarted for at least 3 days after the procedure.
- For bone marrow biopsies that are performed while the subject is on ibrutinib, it is not necessary to hold ibrutinib for these procedures.
- For emergency procedures, ibrutinib should be held after the procedure until the surgical site is reasonably healed, per the appropriate procedural guidelines above.

